## **V. STUDY PROCEDURES**

Lean donors will undergo testing and follow procedures outlined in protocol 2014P002706. Main procedures will occur in the primary 12-week study period; a supplemental week 24 phone-call will be performed for a safety check. In addition, samples of the fecal collection will be stored at -80°C for further microbiome analysis.

Obese recipients will undergo the following procedures:

Phone Screen (10-20 minutes)

Screen Visit (30 minutes)

- Review eligibility and understand/see size of capsules
- Obtain informed consent
- Height, weight measurements to determine eligibility
- Screening labs: Complete blood cell count w/ differential, comprehensive metabolic panel, HIV Ab, HBV sAb/sAg, HCV Ab, fasting insulin and glucose.
- Subjects will be counseled not to start any new major dietary changes, exercise regimens, or medications throughout the primary 12-week study period
- Subjects will be given information about how to perform fecal collections (see Stool Collection document)

Baseline Visit, Week 0 (Day 1: 5 hours, Day 2: 15 minutes, Day 3: 15 minutes)

- Fasting blood samples for measurements of HOMA-IR, lipids, CRP, and HbA1c.
- Women of child bearing potential will have a urine pregnancy test
- Height, weight measurements
- 48-hour food recall
- Whole body DXA scan for body composition analysis
- DXA scan of lumbar spine and hip to assess baseline BMD (optional substudy)
- Fecal collection
- Indirect Calorimetry
- Hyperinsulinemic euglycemic clamp
- After above study procedures are complete, subjects will receive FMT (or placebo) caps, 15 capsules on each of 2 successive days. Note that participants will need to either fast for 4 hours after the clamp or return on the subsequent day for their first capsule administration.

Weeks 1-5 (15 minutes)

- Interval side effect assessment (see Side Effect Assessment document)
- Subjects return for weekly administration of 15 capsules (for a total of 6 weeks, including Week 0)
- Fecal collection at weeks 1, 3 and 5.

Week 6 (5 hours)

- Interval side effect assessment (see Side Effect Assessment document)
- Height, weight measurements
- Women of child bearing potential will have a urine pregnancy test

- Fasting blood samples for measurements of HOMA-IR, lipids, CRP, and HbA1c.
- 48-hour food recall
- Fecal collection
- Whole body DXA scan for body composition analysis
- Fecal collection
- Indirect Calorimetry
- Hyperinsulinemic euglycemic clamp

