#### **D. Safety Monitoring**

Obese recipients will be monitored for clinical safety by history (and standard exams when seen in person) by asking open ended and then directed questions. Subjects will be followed closely, as noted above. Follow up calls made by a study coordinator will be documented and follow up information is reviewed on the same day with a study physician if any symptoms of concern are identified. A physician plan for ongoing follow-up will be noted and implemented. In any case of adverse events identified as grade 2 (moderate severity) an in-person visit with an investigator, either in the GI or ID outpatient practices, will be encouraged.

An AE will be considered related if, in the judgment of the treating physician it is both temporally related to administration of the capsules, and there is no other reasonable alternative explanation, and the AE is not more reasonably attributed to progression of the underlying illnesses.

Any serious adverse event (SAE) assessed as possibly, probably, or definitively related to fecal transplantation will be reported in an expedited fashion to the IRB and FDA. SAE's are defined as any Grade 3 or 4 events as described on the attached AE grading chart, in addition to any event temporally associated with the study procedure that:

- results in death;
- is life threatening (places the subject at immediate risk of death from the event as it occurred);

- requires inpatient hospitalization or prolongation of existing hospitalization;
- results in a persistent or significant disability/incapacity;
- results in a congenital anomaly/birth defect;
- any other adverse event that, based upon appropriate medical judgment, may jeopardize the subject's health and may require medical or surgical intervention to prevent one of the outcomes listed above.

Investigator monitoring with IRB and FDA oversight/reporting is proposed.

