### **E. Study Stop Rules**

The study will have a stop/safety pause in the event of any probably or definitely related SAE, or any apparent transmission of enteric, viral, or other infection from a donor to recipient. (Given the careful screening of donors, we believe this is highly unlikely). A safety pause will also be initiated in the event of a clinically significant complication of ingestion of a large number of capsules, for example medication bezoar (not observed to date in over 125 *C. difficile* patients treated, many with concurrent GI disease). We think this is very unlikely, given that we have demonstrated capsule dissolution occurs reasonably rapidly at neutral pH (i.e. once caps reach the small intestine.) We will track but not specifically stop the study if the following possible expected events occur:

- Transient fever after FMT (up to 102.5° F for 12 hours or less); this is occasionally noted, particularly in younger patients.

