## **VII. RISKS AND DISCOMFORTS**

Capsule administration: The risks of FMT include transmission of an infectious agent from an unrelated individual, or the potential for acquisition of medical illnesses not currently understood to be related to altered GI flora (for example inflammatory conditions, obesity, etc). We believe these risks are low. Other possible risks include nausea, vomiting, diarrhea, fever (all rare based upon experience to date). The risk of bezoar is very low as capsules dissolve promptly in non-acidic environments. We believe there is no risk to placebo capsules which contain gelatin, cocoa, and the same liquid vehicle as FMT caps (IV grade saline and USP glycerol).

Blood drawing: The amount of blood drawn for subjects completing the study is approximately 200 ml over a period of 12 weeks (or 260 mL over 12 months if subjects agree to enroll in optional substudy extension). This does not pose excessive risk to patients and are within Institutional Review Board guidelines. There is a small risk of bleeding, bruising and infection with phlebotomy.

Euglycemic Hyperinsulinemic clamp/insulin: Administration of insulin infusion can cause hypoglycemia. Blood sugar will be monitored every 5 minutes during the insulin clamp, and 20% dextrose is infused per protocol to achieve target blood glucose of 90mg/dL. In the event of hypoglycemia, 50% dextrose is available at the bedside, and a physician or nurse practitioner is present throughout the insulin clamp procedure. There is a minimal risk of burning when using a warming box. This is extremely rare. The warming box has an alarm that prevents the temperature from rising above the set limit.

DXA: Each whole body DXA scan delivers an effective radiation dose of 0.0084 mSv, and the hip and spine DXA scan delivers an additional 0.022mSv. The total amount of

radiation is 0.0472 mSv over 12 weeks, or 0.0776 mSv over 12 months for those participating in the optional study extension.

Indirect Calorimetry: Indirect calorimetry for the measurement of resting energy expenditure is not known to cause any health risks.

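### The outcome criteria for a serious adverse event carry an undefined timing condition, so a late serious outcome not graded 3 or 4 can be left out of the SAE record

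*Combined protocol and SAP*

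**What the plan says.** Section D, Safety Monitoring, gives two alternative routes to SAE status.

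- Severity: "SAE's are defined as any Grade 3 or 4 events as described on the attached AE grading chart". This route has no timing condition.
- Outcome: the list of serious outcomes is introduced by "in addition to any event temporally associated with the study procedure that". The section does not say how close in time an event must be, or whether the procedure meant is capsule intake, the clamp or any study visit.

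The same section has a separate relatedness test, which applies to any adverse event. An event is related if, in the treating physician's judgment, "it is both temporally related to administration of the capsules, and there is no other reasonable alternative explanation", and if it is not better put down to underlying illness. That test also has no window.

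Two rules act on related SAEs. Under section D, an SAE "assessed as possibly, probably, or definitively related to fecal transplantation will be reported in an expedited fashion to the IRB and FDA". Under section E, Study Stop Rules, "The study will have a stop/safety pause in the event of any probably or definitely related SAE".

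Section V, Study Procedures, places capsules at weeks 0 to 5 and adds that "a supplemental week 24 phone-call will be performed for a safety check". Extension participants are followed to month 12.

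**The concern.** Seriousness describes what happened to the participant; relatedness is a judgement about why. A timing condition inside the definition of seriousness lets part of the second question settle the first. An event can then be dropped from the SAE record because someone thought it came too late, before relatedness has been weighed for an SAE.

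This matters because section VI describes the trial as a pilot for feasibility and safety, and section VII names risks that need not appear during dosing: "transmission of an infectious agent from an unrelated individual, or the potential for acquisition of medical illnesses". Some listed outcomes, such as persistent disability or a birth defect, take time to establish, so the timing condition is hardest to meet for outcomes that the plan itself lists. In a randomised comparison, all-cause SAE counts by arm can be read without attributing individual cases, but only if the counts are complete. With 12 participants per arm, one omitted event is visible.

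**Working it through.** The plan states no figure on this point, so the check sets the definition beside the schedule and the rules that use it.

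**Inputs.** Last planned capsules: week 5 (section V). Main follow-up: 24 weeks; extension: 12 months, taken as 52 weeks (section III). Participants outside the extension have no visit between week 12 and the week-24 call (section V).

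**Time after dosing.**

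- Main study: 24 − 5 = 19 weeks; 19/24 = 79%.
- Extension: 52 − 5 = 47 weeks; 47/52 = 90%.
- Week 12 to week 24 without a visit: 24 − 12 = 12 weeks; 12/24 = 50% of main follow-up.

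These shares show how long the undefined condition is open to interpretation. They do not estimate how many events would be lost.

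**How a late event is classified.**

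| Late event | SAE under section D? |
|---|---|
| Graded 3 or 4, any outcome | Yes, whatever its timing |
| Listed outcome, not graded 3 or 4 | Only if judged temporally associated; no window is given |
| Death | Depends on how the chart grades the death or the event leading to it; otherwise as in the row above |

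The gap is the second row, and possibly the third.

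**What follows for each rule.**

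- Expedited reporting needs SAE status and at least possible relatedness.
- The SAE-based pause needs SAE status and probable or definite relatedness.
- Suspected passage of infection from donor to recipient pauses the study without reference to SAE status (section E). So does a clinically significant complication of swallowing many capsules.
- The individual rule (section F) only ends further dosing. Planned dosing is over after week 5, so a late event cannot affect it.
- Relatedness is assessed for adverse events generally, so an event outside the SAE definition still reaches that assessment as an adverse event.

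**Two relatedness scales.** The definition in section D is yes or no, and requires that no reasonable alternative explanation exists. The reporting rule in D uses three levels starting at possible, and the pause rule in E uses the upper two. Read literally, the yes/no definition leaves little room for an event that is only possibly related. The plan does not say how one maps to the other.

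**Scale of one event, as illustration only.** Exact 95% interval for 0/12: upper limit 1 − 0.025^(1/12) = 26.5%. For 1/12 = 8.3%: 0.2% to 38.5% (Clopper-Pearson). The same contrast would arise from any single missed event.

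**The case against.** The strongest reply is that little is lost. Any Grade 3 or 4 event counts at any time, and many serious late events may be graded that high. Adverse events of every kind are asked about at week 12, week 24 and month 12, concerning symptoms from follow-up calls are reviewed by a physician the same day, and Aim 2 makes FMT-related adverse events a secondary outcome with no SAE filter. The reporting and pause rules require relatedness, which has its own temporal test, so an event with no temporal link would probably fail there anyway. The timing phrase could also be read broadly, with a week-20 event still associated with earlier dosing. Finally, section VI specifies no analysis of SAE counts.

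Most of this stands, and it rules out stronger readings. A reader might infer that a death or hospitalisation counts only when it is close to a procedure; the severity route contradicts that. A reader might infer that excluded events escape relatedness assessment and every safety rule; the text contradicts that too, and late transmitted infection has its own pause trigger. Nor can it be said that a week-20 death is not an SAE: that takes the narrowest reading of an undefined phrase and presumes the content of the chart.

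The reply does not remove the gap. Whether a late hospitalisation or disability enters the SAE record should not depend on its symptom grade or on how an undefined phrase is read. That section VI is silent on SAE counts limits the size of the point, but it does not make an incomplete record adequate for a safety pilot.

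**Conclusion.** The point holds in a limited form. The outcome criteria carry an undefined timing condition, and a serious outcome not graded 3 or 4 can be left out of the SAE record during roughly 79% of main follow-up, or 90% with the extension. The number of events affected cannot be estimated from the documents. The main gain from correction is a complete all-cause SAE record by arm; at most, some further events would reach the reporting screen for possible relatedness. The documents do not support the inference that the study pause misses late harm because of this phrase alone.

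The conclusion assumes that the chart does not place every listed outcome at Grade 3 or 4. If it does, the practical gap closes, although the wording would still need correcting. It is worth changing before the safety data are summarised, and it does not bear on the primary outcome or the sample size.

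**What to change.** In section D:

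1. Delete the temporal-association condition from the outcome criteria, so that any event from first capsule to last contact that meets a listed outcome is an SAE, whatever its timing or cause. Define the end by the last contact, because the week-24 and month-12 visits each have a two-month window either way.
2. Keep timing only in the relatedness assessment. Reconcile the yes/no definition with the graded scale used for reporting in D and for the pause in E.
3. Tabulate all SAEs by arm, with relatedness as a separate field.

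One detail needs care: the baseline clamp comes before the first capsule. The section should say that events at that visit are still recorded, so that the change does not drop what the present wording, read broadly, would catch.

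Leave the Grade 3-4 criterion and the triggers in section E as they are. Moving Grade 3-4 events to a separate list would be a matter of preference and could narrow what is now reported or prompts a pause.

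The cost is a wording change, one table, a few more SAE forms and possibly a slightly higher reported SAE count. No new visit is needed, because side effects are already asked about at week 24 and month 12.

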### **E. Study Stop Rules**

The study will have a stop/safety pause in the event of any probably or definitely related SAE, or any apparent transmission of enteric, viral, or other infection from a donor to recipient. (Given the careful screening of donors, we believe this is highly unlikely). A safety pause will also be initiated in the event of a clinically significant complication of ingestion of a large number of capsules, for example medication bezoar (not observed to date in over 125 *C. difficile* patients treated, many with concurrent GI disease). We think this is very unlikely, given that we have demonstrated capsule dissolution occurs reasonably rapidly at neutral pH (i.e. once caps reach the small intestine.) We will track but not specifically stop the study if the following possible expected events occur:

- Transient fever after FMT (up to 102.5° F for 12 hours or less); this is occasionally noted, particularly in younger patients.

### **F. Individual Subject Stop Rules**

By individual, people will not continue dosing if the following happens:

- If the individual is unable to swallow at least 10 capsules at a sitting. Twenty capsules at week 0 and 10 capsules in subsequent weeks are the minimums considered a "full dose" for treatment and analysis purposes.
- If subject requests withdrawal.
- If subject vomits with clinically evident aspiration (by exam or xray; not observed to date)
- If subject experiences an SAE attributed by the study physician to the capsules

### **G. Sample Sharing**

We may share coded samples containing no PHI from both donors and recipients with academic and commercial collaborators researching the microbiome, obesity, insulin sensitivity and probiotics/ecobiotics. Both groups will be notified of this sharing using standard language in the consent forms. We have no current plans or funding for these analyses but wish to keep this option open.

## **VI. BIostatistical Analysis**

Change in insulin sensitivity is the primary outcome and will be compared between placebo and FMT groups over 12 weeks using longitudinal regression models. Secondary outcomes including change in insulin sensitivity, lipids, CRP, and DXA body composition will be similarly investigated. This is a pilot study to determine feasibility

and safety, and to obtain data for power calculations for a larger powered study. After accounting for 15% dropout rate, and assuming a standard deviation of insulin sensitivity of 30-45% and a two-sided alpha of 0.05, this pilot study (n=12 per group) has 80% power to detect a 40-60% difference in insulin sensitivity between groups, and a 30-45% difference from baseline within each group. After accounting for 15% dropout rate, and assuming a standard deviation of weight loss of 5% and a two-sided alpha of 0.05, this pilot study (n=12 per group) has 80% power to detect a 6.6% difference in weight loss between groups, and a 5% difference in weight loss from baseline within each group.

Fecal samples from lean donors and obese recipients will be stored, as noted above. If funding allows in the future, these samples will undergo microbial analysis using 16S ribosomal DNA-based identification and deep sequencing techniques. Changes in the composition of the gut microbiota and metagenomic pathways will be correlated with clinical changes in metabolism.

Bone mineral density (BMD) of the spine, hip, and whole body will be assessed at baseline and at 12 months. This pilot study will provide preliminary data to explore the associations between BMD and gut microbiota prior to manipulation and after FMT.

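### Do the within-arm detectable differences and the full-dose capsule count let the trial claim an FMT effect outside the randomised comparison?

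*Combined protocol and SAP*

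**What the plan says.** Section VI makes change in insulin sensitivity the primary outcome, which "will be compared between placebo and FMT groups over 12 weeks using longitudinal regression models". Secondary outcomes are to be handled in the same way. The power text then gives two detectable differences at the same 80% power, "assuming a standard deviation of insulin sensitivity of 30-45% and a two-sided alpha of 0.05": one between arms and one within each arm, "to detect a 40-60% difference in insulin sensitivity between groups, and a 30-45% difference from baseline within each group". The weight sentence repeats the pattern, with 6.6% between arms "and a 5% difference in weight loss from baseline within each group". The study is described as a pilot for feasibility, safety and the sizing of a later trial.

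Section V.F (Individual Subject Stop Rules) says "Twenty capsules at week 0 and 10 capsules in subsequent weeks are the minimums considered a" full dose, and adds that this holds for treatment and for analysis. It does not say how the analysis uses it. Section VII names nausea, vomiting, diarrhea and fever as possible FMT risks, all rare in experience to date, and says of placebo: "We believe there is no risk to placebo capsules which contain gelatin, cocoa, and the same liquid vehicle as FMT caps". No section names an analysis population.

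**The concern.** A test of change from baseline inside one arm takes no account of the placebo arm. It cannot separate FMT from time, trial participation or placebo response. When such a test is given the same power and alpha as the between-arm contrast, a reader may take it as a second, equal route to a positive result. In a trial of 12 per arm, a significant FMT arm beside a non-significant placebo arm is an easy misreading.

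The capsule count is a separate worry. It is known only after randomisation. If people below the minimum were dropped, and if falling short were commoner under FMT and linked to a worse outcome, the remaining comparison would favour FMT. With no all-randomised set named, nothing in the text explicitly rules this out.

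**Working it through.** **Inputs.** From Section VI: 12 per arm, "After accounting for 15% dropout rate", SD 30-45% for insulin sensitivity and 5% for weight loss, two-sided alpha 0.05, 80% power. Evaluable per arm: 12 × 0.85 = 10.2, taken as 10. The documents give no change common to both arms, so it is assumed over 0 to 1 SD.

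**The plan's own figures** (noncentral t, n = 10 per arm).
- Two-sample t-test: detectable d = 1.325. This gives 1.325 × 30 = 39.7%, 1.325 × 45 = 59.6%, and 1.325 × 5 = 6.62% for weight. Stated: 40-60% and 6.6%.
- Paired t-test: d = 0.996. This gives 29.9%, 44.8%, and 4.98% for weight. Stated: 30-45% and 5%.

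All the figures reproduce.

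**Null trial with a shared change in both arms** (n = 10 per arm). Let b be the chance that the FMT arm improves significantly from baseline and p the two-sided rejection rate in the placebo arm. The arms are independent, so the chance that FMT improves significantly while placebo shows no significant change is b × (1 − p).

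| Shared change (SD) | At SD 30-45% | b | FMT improved, placebo not significant |
|---|---|---|---|
| 0 | 0% | 2.5% | 2.4% |
| 0.25 | 7.5-11% | 10.6% | 9.4% |
| 0.5 | 15-22.5% | 29% | 21% |
| 0.75 | 22.5-34% | 56% | 25% |
| 1.0 | 30-45% | 80% | 16% |

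In simulation at shared changes of 0, 0.25, 0.5 and 1 SD, the between-arm test rejected 5.0% of the time (two-sided), 2.5% in favour of FMT. For a true between-arm effect of 1 SD its power is 56%, against 80% for a within-arm change of that size. That is ordinary arithmetic for the two designs, not an error.

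**Capsule count, if under-dosed FMT participants were dropped** (the plan does not state this).
- Two of 12 removed, each 1 SD worse: the FMT mean moves by 2/12 = 0.167 SD, or 5-7.5 percentage points at SD 30-45%. Type I error becomes about 5.6-6.5%, depending on how the placebo arm is modelled.
- The two worst outcomes removed: the mean moves by about 0.27 SD and type I error is about 11%.
- One to three of 12 removed by a dosing score: the rate in favour of FMT stays at 2.5% if dosing is unrelated to outcome. It is 3.2-4.4% at a correlation of 0.3 and 3.8-6.6% at 0.5.

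**The text side by side.** Section VI lists one kind of analysis, the between-arm comparison, and no within-arm test. Section V.F says when dosing stops; it does not remove anyone from the analysis, and a participant who stops capsules can still attend weeks 6 and 12. The capsule minimum applies to both arms under double blinding (Section IV, Randomization), with placebo capsules of identical appearance (Section V.C). People unable or unwilling to swallow multiple large capsules are excluded at entry.

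**The case for a change.** The strongest case for a change is that power to detect a difference at a given alpha is the power of a test. The within-arm figures match a paired t-test exactly, so someone had that test in mind, and nothing labels it descriptive. Even a modest shared change of 0.25 SD doubles the two-sided within-arm rejection rate, from 5% to 11%. The weight-stability criterion, the counselling against lifestyle change and the repeat HOMA-IR at week 0 limit drift and regression to the mean, but they do not remove placebo response. The capsule count is also the only remark in the document on who counts for analysis, and a pilot meant to size a later trial could pass on a biased estimate.

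Much of this stands as an observation. The plan gives within-arm change no stated role, leaves the analytic use of the full-dose definition unexplained, and names no all-randomised set. A sentence on each would be tidier. It does not show that the planned analysis is wrong. The primary comparison is named and is the randomised one, and no section lets a within-arm result carry an efficacy conclusion. Deleting correct power figures from a pilot would gain nothing.

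**Conclusion.** No change is called for. An analyst who follows Section VI compares the arms as randomised, keeps a 5% two-sided error rate whatever change the arms share, and has the stated 80% power for a 40-60% difference. The within-arm figures are correct side information in a power paragraph.

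The larger error rates rest on conditions the documents do not supply. The 21-25% figures need both arms to improve by 0.5-0.75 SD (15-34% in insulin sensitivity) and a reader who sets the between-arm test aside. The 5.6-11% figures need an outcome-related exclusion in the FMT arm only. With no shared change and no such exclusion there is no inflation. The gap is one of missing detail, which ordinary practice fills: analyse all randomised participants by assigned arm, describe within-arm changes, and keep any full-dose analysis as a sensitivity check. This conclusion would be different if the plan had named a within-arm test as a basis for efficacy or had restricted the primary comparison to full-dose participants. It does neither.

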## II. SPECIFIC AIMS

We propose a randomized placebo-controlled trial to study the impact of gut microbiome alterations on weight, insulin sensitivity, and other important metabolic endpoints.

**Aim 1.** To identify and characterize healthy lean donors from a phenotypic perspective to generate FMT capsules for a clinical trial in obese subjects.

**Aim 2.** To determine the impact of oral capsulized FMT from healthy lean donors on insulin sensitivity in obese adults in a 3-month randomized double-blind placebo-controlled trial. Secondary outcomes include changes in body weight, metabolic markers, and FMT-related adverse events. We hypothesize that FMT recipients will experience an improvement in insulin sensitivity and other metabolic endpoints. An optional extension study will evaluate the durability of gut microbiome change at 12 months.

**Aim 3.** To explore associations between the gut microbiome and bone density.

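### Does Section VI leave change in body weight without a between-arm analysis?

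*Combined protocol and SAP*

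**What the plan says.** The Combined protocol and SAP deals with weight in several places.

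- **Section II, Aim 2**, sets out the secondary outcomes: "Secondary outcomes include changes in body weight, metabolic markers, and FMT-related adverse events". Body weight comes first.
- **Section VI** names change in insulin sensitivity as primary, to be compared between FMT and placebo over 12 weeks with longitudinal regression. The next sentence reads: "Secondary outcomes including change in insulin sensitivity, lipids, CRP, and DXA body composition will be similarly investigated". Weight is not named there, and insulin sensitivity appears a second time.
- **Section VI** then gives weight its own power statement, "assuming a standard deviation of weight loss of 5% and a two-sided alpha of 0.05". With 12 per group and 15% dropout, the study "has 80% power to detect a 6.6% difference in weight loss between groups". The same sentence adds "a 5% difference in weight loss from baseline within each group".
- **Section V** schedules weight measurement at baseline, week 6 and week 12, the same visits as the whole-body DXA scans.

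Nothing in Section VI says which of the two weight figures relates to the efficacy result, or that the within-group figure is descriptive.

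**The concern.** Weight is the only secondary outcome with its own power claim, yet the one sentence that assigns a method to secondary outcomes does not mention it. The one sentence in Section VI that does mention weight sets a between-arm target beside a within-arm target, under one alpha and one power. The within-arm target is the smaller of the two (5% against 6.6%), so it is the easier one to reach. The Aim 2 hypothesis can add to the unease, because it is worded around the treated group alone: "We hypothesize that FMT recipients will experience an improvement in insulin sensitivity and other metabolic endpoints".

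If the weight result were read as change from baseline in the FMT arm, the placebo group would play no part in it. Weight loss common to both arms, from trial participation or closer attention to diet, would be credited to FMT. In a pilot meant to inform a larger trial, that could carry a false signal forward.

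**Working it through.** **1. Do the stated figures hold?** Inputs from Section VI: 12 per group, 15% dropout, SD of weight loss 5%, two-sided alpha 0.05. Completers per arm: 12 × 0.85 = 10.2, taken as 10.

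- Between arms (two-sample t, 18 df): noncentrality = 6.6 / (5 × √(2/10)) = 6.6 / 2.236 = 2.95. Power is 79.7%, and the difference detectable at 80% power is 6.62%. The plan states 6.6%.
- Within an arm (one-sample t on change, 9 df): noncentrality = 5 / (5/√10) = 3.16. Power is 80.3%, and the detectable change is 4.98%. The plan states 5%.
- The insulin-sensitivity figures reproduce on the same basis: 39.7 to 59.6% between arms (stated 40 to 60%) and 29.9 to 44.8% within an arm (stated 30 to 45%).

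The arithmetic is sound, and no wording change would alter it. The within-group figure is also not peculiar to weight, since insulin sensitivity has one in the same form.

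**2. What would reading weight within an arm cost?** Assumption, not in the documents: both arms share a true loss of 0 to 5%, FMT has no effect, and 10 complete per arm with SD 5%. Let p be the chance of a significant loss in one arm. The arms are independent, so a significant loss on FMT but not on placebo has probability p(1 − p).

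| Shared loss | p | p(1 − p) |
|---|---|---|
| 0% | 0.025 | 0.024 |
| 0.5% | 0.047 | 0.045 |
| 1% | 0.082 | 0.075 |
| 2.5% | 0.293 | 0.207 |
| 5% | 0.803 | 0.158 |

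The between-arm test in the same direction stays at 0.025 in every row. If the FMT arm were read entirely alone, the false-positive rate would be p itself. With no shared loss there is no excess under either rule.

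**3. Does the plan use either rule?** Taking the sections together:

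- Section II makes change in body weight a secondary outcome.
- Section VI says secondary outcomes are handled in the same way as the primary, that is, by a longitudinal comparison of FMT with placebo. Its list is introduced as examples and is not closed.
- Section I (contributions of this study) and the opening of Section II both present the effect on weight as a question for a randomized placebo-controlled trial.
- DXA body composition, taken at the same three visits, is expressly in the list. Comparing fat and lean mass between arms while treating weight differently would make no sense.
- No section plans a within-arm test of weight or says that efficacy would be judged by one. A detectable difference is a planning quantity and does not set a decision rule.

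Followed as written, the plan leads to the FMT-placebo difference in weight change. As a two-sample approximation, its 95% CI half-width is t(0.975, 18) × 5 × √(2/10) = 2.101 × 2.236 = 4.70 percentage points. The longitudinal model may give a somewhat different width.

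**4. How likely is a shared loss?** Section III requires stable weight for three months before entry. Section V adds: "Subjects will be counseled not to start any new major dietary changes, exercise regimens, or medications throughout the primary 12-week study period". These measures do not rule out a shared change, but they work against the larger values in the table.

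**The case for a change.** The best case for a change is that the one secondary outcome with a power claim should not get its method by inference, least of all from a list that visibly contains an error. The repeated insulin-sensitivity entry shows that the sentence was not checked. The pilot label does not settle how the within-group figure should be read. Entry criteria and counselling lower the risk of a shared weight change but do not specify an analysis. The correction would cost one list entry and one sentence.

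Part of this stands. The list does omit weight and does repeat the primary outcome, and the within-group figures carry no label. The repeat may stand where weight was meant, or it may refer to the second of the two insulin-sensitivity measures (clamp and HOMA-IR); the text does not say. Neither reading takes weight out of the secondary outcomes.

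The rest does not carry through to a change. The inference is short and has only one sensible end, because the between-arm comparison is the only analysis that Section VI describes. The hypothesis wording is weak support: it does not name weight, and the same Aim 2 paragraph places the question in a placebo-controlled trial. The error rates above nominal belong to rules that appear nowhere in the plan.

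**Conclusion.** No change is needed. The omission of weight from the Section VI list is real and is most likely a clerical slip. The analysis it leaves unsaid is the one analysts would run anyway: change in weight compared between FMT and placebo with the same longitudinal model as the primary outcome. Naming weight in the list would be tidier, but it would alter no analysis, visit, sample size, power figure or type I error.

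The possible harm is 2.4% to 20.7% false signals under a rule of significance on FMT but not on placebo. It depends on two things that the documents do not supply: that rule, and an assumed weight loss shared by both arms. At zero shared loss the excess disappears, and the between-arm test holds at 2.5% in the direction of benefit throughout. The conclusion rests on reading the open-ended Section VI list together with Aim 2, and on 10 completers per arm with an SD of 5% for the figures.
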